3. STUDY DESIGN

This is a prospective, blinded, multi-center study that will be conducted in the US, UK, and Germany. The study will include a minimum of 450 and a maximum of 600 subjects across up to 20 sites with up to 225 min- 300 max subjects in the iTotal CR arm and 225 min- 300 max subjects in the off-the-shelf total knee arm. An additional 25% may be enrolled to account for subject discontinuation.

Subjects will be consecutively recruited in groups of 10, alternating between study arms until enrollment is completed. Once a series of 10 is recruited (subject signed consent and completed pre-op questionnaires), then the next series of 10 is to be recruited.

To ensure that enrollment in each arm remains relatively even, sites assigned odd site numbers will begin by enrolling off-the-shelf subjects and even numbered sites will begin by enrolling ConforMIS subjects. Subjects will be implanted with either an iTotal CR or an off-the-shelf cruciate retaining total knee replacement.

The person administering the functional tests will be blinded. The blind will be maintained for at least one year in order to maintain an objective assessment of each patient's function. Investigators and study staff will make every attempt to maintain the blind by limiting access to study data, x-rays, and other evaluations.

For all surgeries, the preferred surgical approach is to make an incision that is midline or slightly medial to midline, followed by a parapatellar arthrotomy, or a subvastus arthrotomy with prior written approval from Sponsor. The surgeon must use the same approach for all study subjects.

For surgical technique, the off-the-shelf goal is to obtain mechanical alignment.

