6. STUDY DURATION

The study subjects will be required to complete follow-up visits at predetermined intervals for 10 years post-implantation. The in-office follow-up visits will occur at 90 days, 180 days, 1 year, 2 years, 5 years, and 10 years post-implantation. The remaining follow-up data collected at years 3, 4, 6, 7, 8, and 9 may be collected via phone call, mail, or email and does not require an in-office visit.

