10. ENROLLMENT

Potential subjects will be identified by the Investigator or study staff based on patients' clinical and radiographic assessments during regular medical care. The Investigator or study staff will provide study information and the approved Informed Consent Form to all eligible subjects, (determined via Inclusion/Exclusion criteria), as well as answer any questions about the study.

Once the consent form is signed, the subjects will be assigned a unique subject identification number through the EDC system. Once they complete the first set of pre-operative questionnaires, they will be assigned to one of two treatment arms: A) Treatment with the iTotal CR or B) Treatment with an off-the-shelf knee replacement. The site will be instructed to consecutively enroll 10 subjects per treatment arm, alternating between each arm, until enrollment is completed.

The subject identification number will be comprised of a five digit number starting with a two digit site number assigned by ConforMIS at the Site Initiation followed by a three digit subject number, assigned chronologically for the entire study. For example, at site 01, the first subject enrolled will receive number 01-001, followed by 01-002, 01-003, etc.

The Investigator and/or study staff will assess the subject against the Inclusion and Exclusion criteria to determine eligibility. Eligibility includes clinical assessments, radiographic assessments, and a review of the subject's medical history. The radiographic assessments should include:

1. Knee x-ray: 3 views – AP, lateral, sunrise or Merchant
2. Three foot standing x-ray (full length, full weight-bearing film): AP view

If the subject is not eligible to participate in the study, the subject will not be enrolled and is considered a screen failure. All screen failures will be tracked by the site manually in a tracking spreadsheet and electronically in a clinical database. Subject identification numbers for screen failures will not be re-used.

The following Case Report Forms will be completed for all screen failures:

- SUBJECT INFORMATION/MEDICAL HISTORY
- INCUSION/EXCLUSION CRITERIA

If the subject is eligible to participate in the study, they will be assigned to a treatment arm and will be considered enrolled when they are implanted with a device.

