11.7. Year 10 Follow-up Visit (\pm 4 months)

On the 10 year anniversary of the implant surgery, the Investigator or study staff will assess the subject to determine if the iTotal CR or off-the-shelf total knee has been revised.

The site will complete the following Case Report Form:

- FOLLOW UP
- KNEE SOCIETY SCORE (Surgeon portion)
- CONCOMITANT MEDICATIONS (optional)
- PAIN MEDICATIONS
- ADVERSE EVENTS (if any)
- REVISION FORM (if necessary)

The subject will be asked to complete the following function tests and questionnaires to assess long term post-operative pain and function. Note that the subject should return to the clinic to complete these questionnaires.

- THE KNEE INJURY AND OSTEOARTHRITIS OUTCOME SCORE (KOOS)
- KNEE SOCIETY SCORE (Subject portion)
- TIMED “GET UP AND GO”
- 8 METER WALK
- TIMED UP AND DOWN STAIRS

X-rays: None

11.8. **Early Termination Visit**

In the event that the study subject ends their participation in the study prior to the 10 year visit, the investigator or designated study staff will complete the following CRFs:

- SUBJECT DISPOSITION
- CONCOMITANT MEDICATIONS (optional)
- PAIN MEDICATIONS
- ADVERSE EVENTS (if any)
 - REVISION FORM (if necessary)

The Investigator or designated study staff will make every attempt to complete the following evaluations:

- THE KNEE INJURY AND OSTEOARTHRITIS OUTCOME SCORE (KOOS)
- KNEE SOCIETY SCORE (Subject and Surgeon portion)
- TIMED “GET UP AND GO”
- 8 METER WALK
- TIMED UP AND DOWN STAIRS

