15. STATISTICAL METHODS

All statistical processing will be performed using SAS® Version 9.3 or later unless otherwise stated.

For continuous variables, descriptive statistics will include n (number of subjects), mean, standard deviation (SD), median, minimum, and maximum. For categorical variables, the number and percentage of subjects in each category will be presented. Appropriate inferential statistics will be used for the primary and secondary efficacy variables.

Populations

The safety population will be comprised of all subjects for whom the procedure is initiated.

The Full Analysis Set (FAS) will be comprised of all subjects for whom the procedure is completed.

The Per-Protocol (PP) population will include all subjects in the FAS who complete the 1 Year visit without significant protocol violations. The PP population will not include subjects who meet any of the following criteria:

- Violated inclusion/exclusion criteria, without sponsor waiver;
- Did not attend the 1 Year visit
- Out of window at the 1 Year visit by +/- 2 months
- Have undergone a procedure to the contralateral knee which may impact the follow-up assessments

Additional criteria may be added to the list to accommodate for unforeseen events that occur during the conduct of the study that impact efficacy assessments. The PP population will be determined prior to data base lock.

Demographic and Baseline Characteristics

Demographic variables (e.g. age, gender, ethnicity, race) and baseline characteristics will be recorded in the CRF. For continuous variables, comparisons between treatment groups will be

conducted with an analysis of variance (ANOVA). A Cochran-Mantel-Haenszel (CMH) test will be used for testing categorical variables.

Efficacy Analysis

Primary Efficacy Analysis

The absolute change from baseline to 1 Year for each primary endpoint will be analyzed using an analysis of covariance (ANCOVA) with factor of treatment (iTTotal CR, OTS) and the respective baseline score as a covariate. The least squares means will be presented along with the observed means.

Secondary Efficacy Analyses

Secondary endpoints will be analyzed as follows:

- The absolute change from baseline to 1 Year for each subscale of KSS will be analyzed using an analysis of covariance (ANCOVA) with factor of treatment (iTTotal CR, OTS) and the respective baseline score as a covariate. The least squares means will be presented along with the observed means.

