- The absolute change from baseline to 1 Year for each subscale of KOOS will be analyzed using an analysis of covariance (ANCOVA) with factor of treatment (iTTotal CR, OTS) and the respective baseline score as a covariate. The least squares means will be presented along with the observed means.
- Post-operative limb alignment will be dichotomized as in and out of “safe zone” (+/- 3 degrees neutral mechanical axis alignment). The proportion of subjects in each study arm summarized and compared using a CMH test.

Safety Analysis

Procedure-related and device-related adverse events (AEs) occurring during the study will be recorded. For the safety population, AEs will be summarized by study arm, the number of subjects reporting AEs, severity, relationship to procedure, relationship to device, and seriousness.

In addition to overall AE summaries, AEs will be summarized for the following study periods:

- Day of procedure to 6 months post procedure
- Annual summaries (1 Year, 2 Year, etc.) from day of procedure

All serious adverse events (SAEs) will be summarized by study arm, severity, relationship to procedure, and relationship to device. SAEs will also be listed by subject.

All information pertaining to AEs noted during the study will be listed by subject.

The Fisher’s Exact test will be used to compare the proportion of subjects in each study arm who have the following:

- procedure-related AEs
- device-related AEs
- revision procedures

Missing Efficacy Data Imputation

The last observation carried forward (LOCF) method will be used to impute missing efficacy data.

Sample Size Determination

A total sample size of a minimum of 450 and a maximum of 600 subjects will be prospectively enrolled in a consecutive fashion, to each arm of the study (approximately 225-300 in the iTotal CR arm and 225-300 in the OTS arm). To ensure that enrollment in each arm remains relatively even, sites assigned odd site numbers will begin by enrolling off-the-shelf subjects and even numbered sites will begin by enrolling ConforMIS subjects. Based on data from a previous study, it is expected that a minimum of 450 and a maximum of 600 total subjects will provide greater than 80% power for the primary functional endpoint.

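### LOCF is the only rule for missing 1-year efficacy data; while function is still changing, it can bias the arm comparison or dilute an effect that grows over time

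*Combined protocol and SAP*

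**What the plan says.** Section 15, under Missing Efficacy Data Imputation, consists of one sentence: "The last observation carried forward (LOCF) method will be used to impute missing efficacy data". No mixed model, multiple imputation or missing-data sensitivity analysis appears elsewhere. The no-imputation statement in Appendix C covers only the economic sub-study.

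The primary analysis in the same section reads: "The absolute change from baseline to 1 Year for each primary endpoint will be analyzed using an analysis of covariance (ANCOVA", with treatment as factor and the baseline score as covariate. KSS and KOOS subscales are analysed in the same way.

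The values available to carry forward follow from section 6: "The in-office follow-up visits will occur at 90 days, 180 days, 1 year, 2 years, 5 years, and 10 years post-implantation". Section 11.8 adds a possible early-termination assessment: "The Investigator or designated study staff will make every attempt to complete the following evaluations". Whether a pre-operative value may be carried is not stated.

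Of the analysis sets, "The Full Analysis Set (FAS) will be comprised of all subjects for whom the procedure is completed". The per-protocol set excludes, among others, subjects who meet the criterion "Did not attend the 1 Year visit". Neither set is designated as primary, and neither is called a sensitivity analysis for missing data.

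**The concern.** The endpoint is recovery after surgery, and LOCF treats the last value seen as the 1-year value. The protocol's own background (section 1) cites evidence that functional test results got worse after surgery, and gives this as the reason for functional testing. An early value therefore cannot be assumed to stand for 1 Year. If a pre-operative value is carried, the imputed change is exactly zero.

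Unless mean function is flat from the last observed visit to 1 Year, LOCF biases the change within each arm. The errors cancel between arms when missingness is equal in amount and timing and there is no treatment effect. They do not cancel when amount or timing differs, and they attenuate an effect that builds over the year.

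Unequal missingness is plausible here. Allocation is not randomised: "The site will be instructed to consecutively enroll 10 subjects per treatment arm, alternating between each arm, until enrollment is completed". The only person stated to be blinded is the tester: "The person administering the functional tests will be blinded". A difference produced by dropout could then be read as an implant effect, or a real late effect could be diluted, and no planned analysis would reveal which had happened.

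**Working it through.** **Inputs from the documents.** 225 to 300 subjects per arm and power above 80% (section 15); visits at 90 days, 180 days and 1 year (section 6). The extra 25% enrolment in section 3 covers a loss of 1 − 1/1.25 = 20%. It has no time point within the 10-year follow-up, so 20% by 1 year is an upper range, not an estimate.

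**The plan's own figure.** The stated power cannot be reproduced, because effect size, SD, alpha and sidedness are not given. Inverting it at two-sided 0.05 and exactly 80% power gives (1.960 + 0.842) × √(2/225) = 0.264 SD with 225 per arm, and 0.229 SD with 300.

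**Assumed inputs.** Gain means reduction in ALF time. The main case has gains of 2/5/8 s at 90 days/180 days/1 year, SD 6 s, correlation 0.6, 225 per arm, two-sided 0.05, and data missing completely at random within arm. Subjects missing at 1 year were last seen at 180 days, 90 days or pre-op in proportions 50/25/25% if pre-op values may be carried. If only post-operative values are carried, the proportions are 2/3 at 180 days and 1/3 at 90 days.

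**False difference with no true effect.** Let D = 1-year gain − expected carried gain. With the same timing in both arms, false difference = (difference in missing proportion) × D. Rejection rates come from simulating the planned ANCOVA, 5,000 runs per case.

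| Curve; missing | Values carried | D (s) | False difference (s) | Type I error |
|---|---|---|---|---|
| 2/5/8; 10% vs 20% | post-op only | 8 − (2/3×5 + 1/3×2) = 4.0 | 0.10×4.0 = 0.40 | 14% |
| 2/5/8; 10% vs 20% | pre-op allowed | 8 − (0.5×5 + 0.25×2 + 0.25×0) = 5.0 | 0.10×5.0 = 0.50 | 19% |
| 2/5/8; 5% vs 10% | either | 4.0 to 5.0 | 0.05×D = 0.20 to 0.25 | 8% to 9% |
| 2/5/8; 15% in both, last seen at 180 days in one arm and 90 days in the other | post-op only | 3 and 6 | 0.15×(6 − 3) = 0.45 | 15% |
| 2/5/8; 20% in both, same timing | either | equal in both arms | 0 | 4.7% |
| 5/7/8; 10% vs 20% | either | 1.67 to 3.25 | 0.17 to 0.33 (simulated 0.16 to 0.32) | 6% to 10% |
| 6/8/8; 10% vs 20% | post-op only | 8 − (2/3×8 + 1/3×6) = 0.67 | 0.07 | 4.9% |

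On the last curve, allowing the pre-op value gives D = 8 − (0.5×8 + 0.25×6) = 2.5 s and a false difference of 0.25 s (arithmetic only, not simulated). The unstated pre-op rule therefore matters even when recovery is complete by 180 days.

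At 10% vs 20% on the main curve, rejection (post-op only / pre-op allowed) is 11.0%/15.3% at correlation 0.3, 13.7%/19.0% at 0.6 and 18.8%/27.2% at 0.8. At 0.6 the model SE is close to the empirical SE (0.475 vs 0.478 s, and 0.483 vs 0.492 s), so the excess comes from bias. Complete cases in the same runs were within 0.01 s of zero and rejected 4.9% to 5.5% of the time. They are unbiased here because missingness was made completely random within arm.

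**Dilution.** Take a true effect growing 0.40/0.99/1.58 s (1.584 = 0.264 × 6) with 20% missing in both arms. The LOCF effect is 0.8×1.584 + 0.2×(carried effect).

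- Pre-op allowed: carried effect 0.5×0.99 + 0.25×0.40 = 0.595 s, giving 1.39 s.
- Post-op only: carried effect 2/3×0.99 + 1/3×0.40 = 0.793 s, giving 1.43 s.

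Simulated power is 79% to 83%, against 88% for complete cases.

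**Separate check in SD units** (4,000 runs; mean ALF time +0.1/−0.3/−0.8 SD from baseline; 90-day and 180-day values carried equally often).

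- 5% vs 20% missing, no true effect: 0.15 × (0.8 − 0.1) = 0.105 SD, which the simulation reproduces. LOCF rejects 26.5% of the time, observed 1-year data 5.2%.
- Flat course from 90 days, same missingness: bias about 0, rejection 5.6%.
- Effect growing 0/0.1/0.212 SD, 20% missing in both arms: LOCF estimates 0.179 SD with 59% power, observed data 0.212 SD with 70%.
- Effect constant over time: no dilution, and LOCF has more power than observed data (74.5% vs 70.6%).

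**Check of the remedy.** In a further simulation of the seconds-scale cases (2,000 runs each), a likelihood-type estimate using the 90-day and 180-day data was unbiased and slightly more precise than complete cases.

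**The case against.** The strongest reply is that the sizes are assumed and the main curve is steep. Bias needs two conditions together: missingness that differs by arm, and scores that still change after the last visit. On the same curve, 9% vs 11% missing gives only about 0.09 s and a type I error of about 5%. The 5/7/8 curve with 5% vs 10% gives 0.09 to 0.16 s and 5% to 5.5%. Unequal dropout is inferred from the design, both arms have identical visits, and early-termination tests are attempted. All of this stands as a limit on size. It does not remove the defect, because the plan contains nothing that would show whether the harmless case applies.

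The dilution point is the weaker half. With 10% missing in each arm, LOCF power is 87% to 89% against 91% for complete cases. With a proportional effect on the 5/7/8 curve, 20% missing and only post-operative values carried, LOCF has more power than complete cases (91% vs 87%) at an estimate of 1.53 rather than 1.58 s. Material loss needs a late-building effect and high dropout.

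The per-protocol set largely avoids carrying visits forward. But it conditions on who returns at 1 Year, has other exclusions, can gain further criteria, and has no designated role. It is fair to add that the full analysis set is not named as primary either, and that gap should be closed first.

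A repeated-measures model assumes data missing at random, which may fail when a subject cannot do a test. Appendix B stops the stairs trials if the subject is not comfortable repeating them, and ALF sums three tests. This stands, and is why a sensitivity analysis belongs with the model.

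**Conclusion.** The concern holds. LOCF is the sole rule for missing efficacy data on a recovery endpoint, with no sensitivity analysis, in a non-randomised comparison where only the tester is stated to be blinded. The direction of the problem is certain once its conditions are met. The size is not, because trajectory, SD, correlation and missingness by arm are all assumptions. Under them the effect ranges from none (equal missingness, no treatment effect) or 0.07 s (plateau from 180 days, post-operative values only) to a false difference of 0.4 to 0.5 s and up to about four times the nominal type I error (19% against 5%) at 10% vs 20% missing and correlation 0.6. The bias can favour either implant, so LOCF cannot be defended as conservative. It should be fixed, because the rule governs the primary endpoint as well as KSS and KOOS and the remedy is cheap.

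**What to change.** In section 15:

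- Name the primary analysis set. For the full analysis set, replace LOCF for ALF, KSS and KOOS by a mixed model for repeated measures on change from baseline at 90 days, 180 days and 1 Year (treatment × visit, baseline × visit, unstructured covariance), with the 1 Year treatment contrast as the primary result.
- State how an early-termination assessment is assigned to a visit, how ALF is formed when one component is missing, and how revision or death before 1 Year is treated in the analysis.
- Add a delta-adjusted multiple imputation as a sensitivity analysis. Include subjects with no post-operative value, who do not enter the mixed model, and vary delta separately in each arm until the conclusion changes.
- Report the amount and timing of missingness by arm.
- Keep LOCF at most as a supportive analysis, and say there whether a pre-operative value may be carried.

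The cost is SAP wording and standard SAS code, with no new visits or data. The downside is a little more analysis work and reliance on data missing at random, which the delta-adjusted analysis is there to test.

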7.2. Secondary Endpoints

The study secondary endpoints are:

1. The 2011 Knee Society Knee Scoring System[®] (KSS) and/or its subscales at 1 Year post-implantation
2. The Knee Injury and Osteoarthritis Outcome Score (KOOS)
3. Incidence of major procedure-related and device-related complications, including revision rates
4. Post-operative limb alignment

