11. SCHEDULE OF EVALUATIONS BY VISIT

A table displaying the Schedule of Evaluations is in Appendix A. Regardless of treatment arm assigned, subjects will complete each visit in the schedule of evaluations below.

11.1. **Preoperative Visit (Up to 4 months prior to Surgery)**

Many of the screening assessments required to ensure subject eligibility are also considered the pre-operative assessments. The results of the assessments will be captured on the following Screening/Pre-operative Case Report Forms:

- SUBJECT INFORMATION / MEDICAL HISTORY
- CONCOMITANT MEDICATIONS
- PAIN MEDICATIONS
- INCLUSION/EXCLUSION CRITERIA
- KNEE SOCIETY SCORE (Surgeon portion)

The subject will complete the following function tests and questionnaires to assess pain and function as part of their preoperative assessment:

- THE KNEE INJURY AND OSTEOARTHRITIS OUTCOME SCORE (KOOS)
- KNEE SOCIETY SCORE (Subject portion)
- TIMED "GET UP AND GO"
- 8 METER WALK
- TIMED UP AND DOWN STAIRS

X-rays:

- 3 views – AP, lateral, sunrise or Merchant
- Three foot standing x-ray (full length, full weight-bearing film): AP view

11.2. **Surgery Visit (Day 0)**

The Investigator will surgically implant either the iTotal CR in compliance with the ConforMIS surgical training and Instructions for Use, or the off-the-shelf TKR per their surgical training and the manufacturer's Instructions for Use.

The site will complete the following Case Report Forms:

- SURGICAL SUMMARY
- DISCHARGE SUMMARY
- CONCOMITANT MEDICATIONS (optional)
- PAIN MEDICATIONS
- ADVERSE EVENTS (if any occur during surgery through discharge from hospital)

X-rays: None

11.3. **90 Days Follow-up Visit (\pm 14 days)**

At the 90 days follow-up visit, the Investigator or study staff will perform a post-operative knee assessment and identify any adverse events that have occurred since the subject was discharged from the hospital. The site will also collect the Uniform Billing (UB) form from their billing department if contracted with the Sponsor to participate in the Economic Sub-study.

The site will complete the following Case Report Forms:

- FOLLOW UP
- KNEE SOCIETY SCORE (Surgeon portion)

- CONCOMITANT MEDICATIONS (optional)
- PAIN MEDICATIONS
- ADVERSE EVENTS (if any)
 - REVISION FORM (if necessary)

The subject will complete the following function tests and questionnaires to assess post-operative pain and function:

- THE KNEE INJURY AND OSTEOARTHRITIS OUTCOME SCORE (KOOS)
- KNEE SOCIETY SCORE (Subject portion)

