- TIMED “GET UP AND GO”
- 8 METER WALK
- TIMED UP AND DOWN STAIRS

X-rays:

- 3 views – AP, lateral, sunrise or Merchant*
- Three foot standing x-ray (full length, full weight-bearing film): AP view*

**(Depends on hospital standards. Protocol requires only one set of post-op x-rays at either 90 or 180 days)*

11.4. **180 Days Follow-up Visit (± 21 days)**

At the 180 days follow-up visit, the Investigator or study staff will perform knee assessments and identify any adverse events that have occurred since the last visit.

The site will complete the following Case Report Forms:

- FOLLOW UP
- KNEE SOCIETY SCORE (Surgeon portion)
- CONCOMITANT MEDICATIONS (optional)
- PAIN MEDICATIONS
- ADVERSE EVENTS (if any)
 - REVISION FORM (if necessary)

The subject will complete the following function tests and questionnaires to assess post-operative pain and function:

- THE KNEE INJURY AND OSTEOARTHRITIS OUTCOME SCORE (KOOS)
- KNEE SOCIETY SCORE (Subject portion)
- TIMED “GET UP AND GO”
- 8 METER WALK
- TIMED UP AND DOWN STAIRS

X-rays:

- 3 views – AP, lateral, sunrise or Merchant*
- Three foot standing x-ray (full length, full weight-bearing film): AP view*

**(depends on hospital standards. Protocol requires only one set of post-op x-rays at either 90 or 180 days)*

11.5. **Year 1, 2, and 5 Follow-up Visits (± 2 months)**

At the 1 year, 2 year, and 5 year follow-up visits, the Investigator or study staff will perform a knee assessment and identify any adverse events that have occurred since the subject's last visit.

The site will complete the following Case Report Forms:

- FOLLOW UP
- KNEE SOCIETY SCORE (Surgeon portion)
- CONCOMITANT MEDICATIONS (optional)
- PAIN MEDICATIONS
- ADVERSE EVENTS (if any)
 - REVISION FORM (if necessary)

The subject will complete the following function tests and questionnaires to assess post-operative pain and function:

- THE KNEE INJURY AND OSTEOARTHRITIS OUTCOME SCORE (KOOS)
- KNEE SOCIETY SCORE (Subject portion)
- TIMED "GET UP AND GO"
- 8 METER WALK
- TIMED UP AND DOWN STAIRS

X-rays: None

11.6. Year 3, 4, 6, 7, 8, and 9 Follow-up Visits (\pm 3 months)

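### Read literally, the blanket LOCF rule leaves only the pre-operative angle to stand in for a missing post-operative limb alignment value

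*Combined protocol and SAP*

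**What the plan says.** Section 7.2 lists "Post-operative limb alignment" as the fourth secondary endpoint. Section 15 analyses it in the list under Secondary Efficacy Analyses, introduced by "Secondary endpoints will be analyzed as follows". The definition is a status after surgery, not a change from baseline: "Post-operative limb alignment will be dichotomized as in and out of" a zone of 3 degrees either side of neutral mechanical axis, with the arms compared by a CMH test.

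The only missing-data rule for efficacy data in Section 15 is "The last observation carried forward (LOCF) method will be used to impute missing efficacy data". It names no exception and does not say whether a pre-operative value may be carried. The statement in Appendix C that nothing is imputed belongs to the economic sub-study.

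On films, Section 11.1 calls for a pre-operative "Three foot standing x-ray (full length, full weight-bearing film): AP view". Sections 11.3 and 11.4 list the same view with the note "Protocol requires only one set of post-op x-rays at either 90 or 180 days". Section 11 and Appendix A schedule no x-ray at surgery or from year 1 to year 10, and the early termination visit (11.8) lists none.

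On the analysis set: "The Full Analysis Set (FAS) will be comprised of all subjects for whom the procedure is completed". A subject without a post-operative film therefore stays in it.

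**The concern.** LOCF needs an earlier observation of the same quantity. For the function tests and questionnaires at 1 year, the carried value can be a 90-day or 180-day post-operative measurement. For alignment under the minimum schedule there are two time points, one on each side of the operation. If the second is missing, only the first remains, and the operation changes that angle.

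The misclassification can go either way. A knee at 8 degrees varus before surgery and 1 degree after it, with the film missed, is truly in zone but scored out. A knee at 2 degrees before and 5 degrees after, with the film missed, is truly out but scored in.

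At stake is one secondary comparison. The reported in-zone proportion would partly describe knees before surgery. If film completion differed by arm, the CMH test could show a difference that reflects who was filmed rather than which implant was used.

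**Working it through.** **Step 1: trace the rule through the schedule.** The plan gives no figure for the alignment endpoint, so there is nothing of its own to reproduce. (The power claim of more than 80% concerns the primary endpoint only.)

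| Situation | Alignment values on file | Value used under literal LOCF |
|---|---|---|
| Film at 90 or 180 days | pre-operative and post-operative | post-operative: correct |
| No film at 90 or 180 days | pre-operative only | pre-operative: not the endpoint |

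**Step 2: formula for the bias.** Let p be the true post-operative in-zone rate, q the pre-operative in-zone rate, and m the share of subjects without a post-operative film. Films are taken to be missing at random.

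- Reported rate = (1 − m)p + mq
- Bias = −m(p − q)

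The bias is zero if m = 0 and downward only if q < p. It depends on both m and p − q.

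**Step 3: assumed inputs.** From the documents: 225 per arm (the planned minimum) and exclusion of fixed varus or valgus deformity above 15 degrees. Everything else is assumed. For q, a Normal pre-operative axis truncated at 15 degrees either side gives these shares within 3 degrees of neutral:

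| Mean varus / SD (degrees) | In zone before surgery |
|---|---|
| 0 / 6 | 38.8% |
| 3 / 6 | 35.0% |
| 5 / 6 | 29.2% |
| 6 / 5 | 24.7% |
| 8 / 5 | 15.7% |

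I use q = 15% to 39%, and p = 80% with a range of 70% to 90%.

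**Step 4: equal missingness, m = 10% in both arms, p = 80%.**

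- q = 15%: 0.9 × 0.80 + 0.1 × 0.15 = 73.5%
- q = 39%: 0.9 × 0.80 + 0.1 × 0.39 = 75.9%

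**Step 5: unequal missingness, 5% v 15%, no true difference.** The false gap is (0.15 − 0.05)(p − q). Rejection is for a two-sided 5% test of two proportions (normal approximation, 225 per arm).

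| p | q | Reported, 5% missing | Reported, 15% missing | False gap (points) | Rejection |
|---|---|---|---|---|---|
| 80% | 15% | 76.75% | 70.25% | 6.5 | about 35% |
| 80% | 25% | 77.25% | 71.75% | 5.5 | about 27% |
| 80% | 39% | 77.95% | 73.85% | 4.1 | about 17% |
| 70% | 39% | 68.45% | 65.35% | 3.1 | about 11% |
| 90% | 15% | 86.25% | 78.75% | 7.5 | about 55% |

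The nominal rejection rate is 5%. At 300 per arm and p = 80%, the figures for q = 15% and q = 39% rise to about 44% and 22%, because a larger sample detects the false gap more readily.

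**The case against.** The strongest reply is that Section 15 never says a baseline value is carried. The variable is named as post-operative alignment, a pre-operative film is not an observation of it, and a careful statistician could leave the value missing. That is a sensible choice, but the plan does not state it. It departs from a mandatory instruction to impute, and it might be made only after the data are seen. So a reader might infer that the plan expressly prescribes carrying the pre-operative film. The documents do not go that far. They give a blanket rule that, applied literally, leaves no other value to use.

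A reader might also infer that the safe-zone proportion will be too low in both arms. That requires missing films in both arms and a lower in-zone rate before surgery than after. The documents give neither rate, and individual errors can go in either direction. Nor is it right to say that the untreated deformity is always what gets counted: under the assumptions above, 16% to 39% of knees are already in zone before surgery.

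Exposure is also limited. A film at either 90 or 180 days suffices, sites may be queried for missing data (Section 13), and the oversight committee may exclude a site with incomplete data (Section 9). These provisions reduce the number of missing films but do not say how a missing one is handled. Finally, the 5% v 15% imbalance has no basis in the documents, so the rejection rates show what could happen, not what is expected.

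**Conclusion.** The point holds as a conditional one. On a literal reading, the LOCF sentence reaches an endpoint for which the only value it can carry predates the operation. This is a stated rule that yields a value of the wrong quantity, not merely a missing detail.

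Its size cannot be fixed from the documents. Under the assumed rates, 10% missing films would lower a true 80% by about 4 to 6.5 points. A 5% v 15% imbalance would create a false gap of about 4 to 6.5 points with rejection of about 17% to 35% at 225 per arm; over a true 70% to 90% the range is 3.1 to 7.5 points and 11% to 55%. These figures are illustrative and assume films missing at random. One secondary endpoint is affected. The primary ALF analysis is not. The change is worth making because it is cheap and settles the handling before analysis.

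**What to change.** Add to the missing-data paragraph of Section 15: *LOCF does not apply to post-operative limb alignment; no pre-operative radiograph will be used as a post-operative value.*

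Compare the safe-zone proportion among subjects with a post-operative long-leg film, and report the number without one by arm. Add a simple sensitivity analysis, such as best-case and worst-case bounds: with 10% missing and 80% in zone among those filmed, an arm's proportion lies between 0.9 × 0.80 = 72% and 72% + 10% = 82%. Multiple imputation from pre-operative alignment within arm is optional.

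The cost is a sentence or two of text and one small table, with no new data. The downside is that the comparison rests on fewer subjects, and it relies on those filmed being representative, which the bounds are there to test.
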